9.3 Treatment Administration

Subjects will be randomized to treatment group prior to surgery, no sooner than 10 business days prior to Visit 00. The lens to which the subject is randomized, must be implanted in both eyes. [REDACTED]

[REDACTED]

Each study surgeon will follow his/her **routine** cataract procedure for all study surgeries. It is permitted to have 1 study-trained surgeon at each site perform IOL implantations. For surgeons with experience prior to the start of the trial, femtosecond laser-assisted cataract surgery (FLACS) is permitted, however it is **NOT** required. The laser may **ONLY** be used for the following:

- Primary and sideport incisions
- Capsulorhexis
- Lens fragmentation

Use of any intraoperative power assessment is not permitted during surgery.

9.4 Treatment Assignment / Randomization

Subjects will be randomized in a 1:1:1 ratio to receive treatment with the VIVITY or the SYMFONY or the AT LARA IOLs.

[figure not shown]
Only after signing the ICF, will a subject be assigned a subject number by the electronic data capture system.

A randomization list will be generated using a validated system that automates the random assignment of treatment arms to randomization numbers in the specified ratio. Subjects will be assigned treatment according to the randomization list uploaded in the IRT system. The randomization list will be generated and maintained by the Study Sponsor.

No sooner than 10 business days of Visit 00, each eligible subject will be randomized via the IRT system to one of the treatment arms. The Investigator or unmasked delegate will access the respective system after confirming that the subject meets all the eligibility criteria. A randomization number will be automatically assigned to the subject according to the subject randomization list but will not be communicated to the site user. The IRT system will inform the site user of the treatment assignment.

9.5 Treatment Masking

This study is double-masked (effectiveness assessor and subject) with subjects randomized for bilateral implantation with one of the three studied IOLs.

The effectiveness assessor and subject masking will be maintained throughout the conduct of the study until all study data is validated and final database lock occurs. [REDACTED]

[REDACTED]

[REDACTED]

[REDACTED]

9.6 Accountability Procedures

Upon receipt of test article from the Sponsor, the Investigator or delegate must conduct an inventory of all lenses by serial number, complete study-specific confirmation of receipt procedures [REDACTED] and retain any required documentation in the Investigator's clinical study records.

For all IP (test and control articles) the Investigator or delegate must maintain records of use and implantation for each subject throughout the study. [REDACTED]

[REDACTED]

Return to the Study Sponsor recoverable test articles associated with a device deficiency. Refer to Section 11 of this protocol for additional information on the reporting of device deficiencies [REDACTED]

[REDACTED]

At the conclusion of the study, the Investigator will be responsible for returning all used and unused study supplies (including test and control articles) as instructed by the Sponsor.

[REDACTED]

9.7 Changes to concomitant medications, treatments/ procedures

After the subject is enrolled into the study, the Investigator must instruct the subject to notify the study site about:

- Any new medications (include herbal therapies, vitamins, and all over-the-counter as well as prescription medications).

Note: Throughout the subject's participation, obtain information on any changes in medical health and/or the use of concomitant medications.

- Alterations in dose or dose schedules for current medications,
- Any medical procedure or hospitalization that occurred or is planned
- Any non-drug therapies (including physical therapy and blood transfusions).

The Investigator must document this information in the subject's case history source documents.

10 STUDY PROCEDURES AND ASSESSMENTS

The following section outlines the assessments performed in this clinical study. The Investigator is responsible for ensuring responsibilities for all procedures and assessments are delegated to appropriately qualified site personnel.

Assessments [REDACTED] are outlined in Table 3–1, Schedule of Study Procedures and Assessments.

During the course of the study, it is possible that the window of visits may overlap; in such cases the subject may complete both visits on the same day at the discretion of the Investigator (and the data would be entered for each respective visit in EDC).

10.1 Informed Consent and Screening

The Investigator or delegate must explain the purpose and nature of the study, and have the subject or legally authorized representative read, sign, and date the IRB/IEC-approved informed consent document. The subject must sign the ICF **before** any study-specific procedures or assessments can be performed, including study-specific screening procedures. (Note that data from exams and assessments specified in Section 10.2.1 that were completed within 30 days of screening can be used as per discretion of Investigator.)

Additionally, the individual obtaining consent from the subject and a witness, if applicable, must sign and date the informed consent document. The subject should be provided with

enough time for his/her decision on participation in the study, and should have options to discuss with his/her family members or relatives about the participation in the investigation.

The Investigator or delegate must provide a copy of the signed document to the subject and place the original signed document in the subject's chart, or provide documentation as required by local regulations. Note that the applicable privacy regulation requirements must be met.

10.2 Visits and Examinations

Data from the Investigator's previous routine clinical evaluation (ie, slit-lamp examination, dilated fundus examination, IOP, biometry and keratometry) may fulfill Visit 0 requirements, if the data comply with the following:

1. meet the conditions of this protocol [REDACTED]
2. apply for all 3 IOLs being tested; and
3. were collected within 30 days of screening.

10.2.1 Visit 0: Preoperative Screening Visit (-28 - 0 Days Prior to Visit 00)

1. After the subject signs the consent, assess **inclusion/exclusion criteria**. The subject must meet all inclusion criteria and must not meet any exclusion criteria prior to surgery.
2. Obtain the subject's **demographic** information (including age, race and sex), **medical/ocular history** within 30 days prior to signing the ICF, and **concomitant medications** for ocular and non-ocular conditions used by the subject at the time of the visit.
3. Perform a **urine pregnancy** test, IF the subject is a woman of childbearing potential (defined as all women who are physiologically capable of becoming pregnant and who are not postmenopausal for at least 1 year or are less than 6 weeks since sterilization).
4. Adjust room to **photopic lighting** for distance (4 m).
5. Perform **manifest refraction** (OD, OS).
6. Measure and record monocular **BCDVA** at 4 m (OD, OS).
7. Measure optical **keratometry** and optical **biometry** according to the Investigator's standard of care noting all available measurements including corneal thickness, crystalline lens thickness, white-to-white, anterior chamber depth (ACD) and axial length (AL).

[REDACTED]

- 8. **Select and document** the subject's required lens power for each of the 3 IOLs (VIVITY, SYMPHONY and AT LARA).

[REDACTED]

[REDACTED]

- 9. Perform **slit-lamp examination** of the anterior segment of both eyes.

[REDACTED]

- 10. Subject **questionnaires** completed: QUID

[REDACTED]

- 13. Perform a **dilated fundus** examination of both eyes. *Note: if this exam was completed on this subject ≤ 30 days prior to the date of screening that data may be used (per the Investigator's discretion) and this test is not required to be repeated.*

- 14. Record any **adverse events**.

- 15. Ensure that all inclusion/exclusion criteria have been met and that all preoperative screening assessments have been performed. Upon meeting eligibility criteria, subjects will be scheduled for surgery.

NOTE: The eye with the worse BCDVA will be the first eye implanted. If the distance BCDVA in both eyes is the same, the right eye (OD) will be implanted first.

10.2.2 Visit 00: Surgery Visit 1st Eye (0-28 days after Visit 0)

- 1. In preparation for the operative visit, randomize the subject. It is recommended that subjects are contacted prior to randomization to 1) confirm willingness to continue trial participation, and 2) confirm scheduled surgical date and time.

- 
2. Record **operative eye**.
 3. Record changes in **medical/ocular history** and **concomitant medications** for ocular and non-ocular **conditions**.
 4. Verify **inclusion/exclusion criteria**. Subjects must meet all requirements to proceed to surgery.
 5. Prepare subject for surgery in accordance to site specific operating procedures and ensure that all IOL power calculations have been completed.
 6. Perform **surgery** and **implantation** with the IOL to which the subject was randomized.
 7. Record any surgical problems, complications, or other procedures (including SSIs) that occurred during surgery. Other procedures include those performed outside of routine cataract surgery. **Other planned procedures at the time of surgery are exclusionary**.
 8. Record **final incision size**.
 9. Record **lens information** that is located on the IOL sticker. Both successful and aborted (if applicable) test and control article information should be recorded.
 10. Assess if any **IOL damage** has occurred. If an IOL is damaged/defective and not implanted, it must be returned to the respective manufacturer as a **device deficiency**.
 11. Record any **surgical problems, complications** or **secondary surgical interventions** for the operative eye, if applicable.
 12. Record any **adverse events**.
 13. Record any **device deficiencies**.

10.2.3 Visit 1: Postoperative for 1st Eye (1-2 days after Visit 00)

1. Record changes in **medical/ocular history** and **concomitant medications** for ocular and non-ocular conditions.
2. Perform **slit-lamp examination** of the anterior segment. *Note that only unmasked site staff can perform slit-lamp exam.*
3. Record **IOL observations**, if any.
4. Record **lens decentration and/or tilt**, if applicable.

5. Record **subjective posterior capsule opacification** and information for any **posterior capsulotomy** that has occurred since surgery, if applicable for operative eye.
6. Perform **tonometry** to measure the intraocular pressure.
7. Record **secondary surgical interventions** that have occurred since surgery, if applicable.
8. Record any **adverse events**.
9. Record any **device deficiencies**, if applicable.

10.2.4 Visit 2: Postoperative for 1st Eye (7-14 days after Visit 00)

1. Record changes in **medical/ocular history** and **concomitant medications** for ocular and non-ocular conditions.
2. Adjust room to **photopic lighting for distance** at 4 m.
3. Perform **manifest refraction** at 4 m.

- [REDACTED]
5. Perform **slit-lamp examination** of the anterior segment. [REDACTED]
[REDACTED]
 6. Record **IOL observations**, if any.
 7. Record **lens decentration and /or tilt**, if applicable.
 8. Record **subjective posterior capsule opacification** and information for any **posterior capsulotomy** that has occurred since surgery, if applicable for operative eye.
 9. Perform **tonometry** to measure the intraocular pressure.
 10. Record **secondary surgical interventions** that have occurred since surgery, if applicable.
 11. Record any **adverse events** (both volunteered and elicited).
 12. Record any **device deficiencies**, if applicable.

10.2.5 Visit 00A: Surgery Visit 2nd Eye (7-21 days after Visit 00)

Follow all procedures listed in Section 10.2.2, starting with Step 2, for the 2nd operative eye.

10.2.6 Visit 1A: Postoperative for 2nd Eye (1-2 days after Visit 00A)

Follow all procedures listed in Section 10.2.3 for the 2nd operative eye.

10.2.7 Visit 2A: Postoperative for 2nd Eye (7-14 days after Visit 00A)

Follow all procedures listed in Section 10.2.4 for the 2nd operative eye.

10.2.8 Visit 3A: Postoperative for Both Eyes (30-60 days after Visit 00A)

1. Subject **questionnaires** completed: QUID, [REDACTED].
2. Record changes in **medical/ocular history** and **concomitant medications** for ocular and non-ocular conditions.
3. Adjust room to **photopic lighting for distance** at 4 m.
4. Perform **manifest refraction** at 4 m for each eye.

7. Perform **slit-lamp examination** of the anterior segment. *Note that only unmasked site staff can perform slit-lamp exam.*
8. Record **IOL observations**, if any.
9. Record **lens decentration and /or tilt**, if applicable.
10. Record **subjective posterior capsule opacification** and information for any **posterior capsulotomy** that has occurred since surgery, if applicable.
11. Perform **tonometry** to measure the intraocular pressure.
12. Record **secondary surgical interventions** that have occurred since surgery, if applicable.
13. Record any **adverse events** (both volunteered and elicited).
14. Record any **device deficiencies**, if applicable.

10.2.9 Visit 4A: Postoperative for Both Eyes (70-100 days after Visit 00A)

Note: Due to the large number of assessments and exams indicated for this visit the subject may be allowed to complete Visit 4A in two sessions (both occurring between 70-100 days after Visit 00A).

1. Subject **questionnaires** completed: QUID, [REDACTED].
2. Record changes in **medical/ocular history** and **concomitant medications** for ocular and non-ocular conditions

[REDACTED]

[REDACTED]

6. Perform **manifest refraction** at 4 m. [REDACTED]
[REDACTED].

[REDACTED]

[REDACTED]

[REDACTED]

[REDACTED]

[REDACTED]

[REDACTED]

[REDACTED]

[REDACTED]

[REDACTED]

[REDACTED]

[REDACTED]

17. Measure optical **keratometry** and optical **biometry** according to the Investigator's standard of care noting all available measurements including anterior chamber depth (ACD) and axial length (AL), corneal thickness, crystalline lens thickness and white-to-white.

18. Perform **slit-lamp examination** of the anterior segment. *Note that only unmasked site staff can perform slit-lamp exam.*

19. Record **IOL observations**, if any.

20. Record **lens decentration and /or tilt**, if applicable.

21. Record **subjective posterior capsule opacification** and information for any **posterior capsulotomy** that has occurred since surgery, if applicable.

22. Perform **tonometry** to measure the intraocular pressure.

23. Record **secondary surgical interventions** that have occurred since surgery, if applicable.

24. Record any **adverse events** (both volunteered and elicited).

25. Record any **device deficiencies**, if applicable.

10.2.10 Visit 5A: Postoperative for Both Eyes (120-180 days after Visit 00A)

1. Subject **questionnaire** completed: QUVID.
2. Record changes in **medical/ocular history** and **concomitant medications** for ocular and non-ocular conditions.
3. Adjust room to **photopic lighting for distance** at 4 m.
4. Perform **manifest refraction** at 4 m.

[REDACTED]

[REDACTED]

[REDACTED]

7. Perform **slit-lamp examination** of the anterior segment. [REDACTED]

[REDACTED]

8. Record **IOL observations**, if any.
9. Record **lens decentration and /or tilt**, if applicable.
10. Record **subjective posterior capsule opacification** and information for any **posterior capsulotomy** that has occurred since surgery, if applicable.
11. Perform **tonometry** to measure the intraocular pressure.
12. Record **secondary surgical interventions** that have occurred since surgery, if applicable.
13. Record any **adverse events** (both volunteered and elicited).
14. Record any **device deficiencies**, if applicable.

10.2.11 Unscheduled Visits

If a subject is examined more than once during any of the scheduled follow-up periods, or between scheduled follow-up periods due to a potential issue, an unscheduled visit form should be completed, reporting any study parameters or any relevant data collected at this visit. If, during the visits specific for the second eye, a clinical observation is made on the first eye implanted, an unscheduled visit form should be completed to record the first eye data. The following exams and assessments are recommended and should be completed as per the Investigator's expert opinion; in the event this is not possible, the data that is available should be reported.

1. Record changes in **medical/ocular history** and **concomitant medications** for ocular and non-ocular conditions.
2. Perform **manifest refraction** at 4 m.

4. Perform **slit-lamp examination** of the anterior segment of both eyes. *Note that only unmasked site staff can perform slit-lamp exam except in cases of medical emergency.*
5. Record **IOL observations**, if any for the operative eye(s).
6. Record **lens decentration and/or tilt**, if applicable.
7. Record **subjective posterior capsule opacification** and information for any **posterior capsulotomy** that has occurred since surgery, if applicable for operative eye(s).
8. Perform **tonometry** to measure the intraocular pressure of both eyes.
9. Perform a **dilated fundus** examination of both eyes.
10. Record **secondary surgical interventions** for the operative eye(s) that have occurred since surgery, if applicable.
11. Record any **adverse events** (both volunteered and elicited).
12. Record any **device deficiencies**, if applicable.

10.3 Discontinued Subjects

10.3.1 Screen Failures

Subjects who were excluded from the study after signing the informed consent and prior to randomization are considered screen failures. The Investigator must document the reason for screen failure in the subject's case history source documents.

Subject numbers must not be re-used.

10.3.2 Discontinuations

Discontinued subjects are individuals who voluntarily withdraw or are withdrawn from the study by the Investigator after randomization.

Subject numbers of discontinued subjects must not be re-used.

Subjects may discontinue from study or study treatment at any time for any reason. Subjects may also be discontinued from study treatment at any time if, in the opinion of the Investigator, continued treatment poses a risk to their health.

If a subject discontinues from study treatment, every effort must be made to keep the subject in the study and to continue with the study assessments as specified in the schedule of study procedures and assessments until the final visit.

The Investigator must document the reason for study or treatment discontinuation in the subject's case history source documents.

To ensure the safety of all subjects who discontinue early, Investigators must assess each subject and, if necessary, advise them of any therapies and/or medical procedures that may be needed to maintain their health.

10.3.3 Schedule of Procedures and Assessments for Subjects Discontinued from Investigational Product

Subjects who discontinue IP (ie, have study lens explanted), will continue in the study through Visit 5A and be followed for safety. At minimum, safety examinations must include the assessments associated with appropriate medical care. Standard post-surgical assessments are bulleted below:

- UCDVA and/or BCDVA
- Slit-lamp Examination
- Dilated Fundus Examination

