Key words	
• Cataracts• Intraocular lens• IOL• Extended depth of focus• Presbyopia• Australia• New Zealand• Visual disturbances
 	 

Table 3-1 Schedule of Study Procedures and Assessments

Visit	Visit 0	Visit 00	Visit 1	Visit 2	Visit 00A	Visit 1A	Visit 2A	Visit 3A	Visit 4A ¹	Visit 5A	Unscheduled visit
Eye	Both Eyes	1 st Eye	1 st Eye	1 st Eye	2 nd Eye	2 nd Eye	2 nd Eye	Both Eyes	Both Eyes	Both Eyes	N/A
Day Number	Day -28 to 0	Day 0	Day 1-2 Post Visit 00	Day 7-14 Post Visit 00	Day 7-21 Post Visit 00	Day 1-2 Post Visit 00A	Day 7-14 Post Visit 00A	Day 30-60 Post Visit 00A	Day 70-100 Post Visit 00A	Day 120-180 Post Visit 00A	N/A
General Assessments and Procedures											
Informed Consent	X										
Demographics	X										
Medical History	X										
Concomitant Medications	X	X	X	X	X	X	X	X	X	X	X
Inclusion/Exclusion	X										
Urine Pregnancy Test ²	X										
Ophthalmic Assessments											
Questionnaires											
• QUID (for visual disturbance)	X							X	X	X	
• [REDACTED]											
• [REDACTED]											

Printed By:

Print Date:

Visit	Visit 0	Visit 00	Visit 1	Visit 2	Visit 00A	Visit 1A	Visit 2A	Visit 3A	Visit 4A ¹	Visit 5A	Unscheduled visit
Eye	Both Eyes	1 st Eye	1 st Eye	1 st Eye	2 nd Eye	2 nd Eye	2 nd Eye	Both Eyes	Both Eyes	Both Eyes	N/A
Day Number	Day -28 to 0	Day 0	Day 1-2 Post Visit 00	Day 7-14 Post Visit 00	Day 7-21 Post Visit 00	Day 1-2 Post Visit 00A	Day 7-14 Post Visit 00A	Day 30-60 Post Visit 00A	Day 70-100 Post Visit 00A	Day 120-180 Post Visit 00A	N/A
[REDACTED]	■							■	■		
Biometry (collect all available measurements including ACD, AL, keratometry, corneal thickness, crystalline lens thickness, white-to-white)	X ³								X		
Manifest Refraction	X			X			X	X	X	X	(✓)
[REDACTED]											
[REDACTED]									■		
[REDACTED]	■			■			■	■	■	■	■
[REDACTED]									■		
[REDACTED]									■		
[REDACTED]									■		
[REDACTED]									■		

Printed By:

Print Date:

Visit	Visit 0	Visit 00	Visit 1	Visit 2	Visit 00A	Visit 1A	Visit 2A	Visit 3A	Visit 4A ¹	Visit 5A	Unscheduled visit
Eye	Both Eyes	1 st Eye	1 st Eye	1 st Eye	2 nd Eye	2 nd Eye	2 nd Eye	Both Eyes	Both Eyes	Both Eyes	N/A
Day Number	Day -28 to 0	Day 0	Day 1-2 Post Visit 00	Day 7-14 Post Visit 00	Day 7-21 Post Visit 00	Day 1-2 Post Visit 00A	Day 7-14 Post Visit 00A	Day 30-60 Post Visit 00A	Day 70-100 Post Visit 00A	Day 120-180 Post Visit 00A	N/A
[REDACTED]											
[REDACTED]									■		
[REDACTED]									■		
[REDACTED]									■		

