5.2 Purpose of the Study

This postmarket study is intended to support scientific messaging and to compare the visual disturbance profile of the non-diffractive VIVITY IOL to two marketed diffractive EDF IOLs, SYMFONY and AT LARA.

[REDACTED]

Results of the study are intended for publication and presentation at ophthalmology conferences globally.

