4.3.2 Secondary Effectiveness Analyses

For each comparator, if the primary effectiveness hypothesis is not successful, no hypothesis test for secondary effectiveness endpoints will be further conducted for that comparator. If the primary effectiveness hypothesis is successful, hypotheses for glare will first be tested. If the hypothesis for glare is successful, the hypothesis for starbursts will be tested.

The superiority hypothesis for each comparator will be evaluated using the Miettinen-Nurminen method (1985). The superiority hypothesis will be deemed supported if the lower limit of the two-sided 97.5% confidence interval exceeds zero. Main analysis will be based on AAS. [REDACTED]

Success on the secondary hypothesis tests, sequentially for glare then starbursts, will be concluded independently for between VIVITY and SYMFONY, and between VIVITY and AT LARA.

[REDACTED]

[REDACTED]

[REDACTED]

[REDACTED]

[REDACTED]

[REDACTED]

- [REDACTED]
- [REDACTED]
- [REDACTED]
- [REDACTED]

[REDACTED]

[Redacted text block]

[Redacted text block]

[Redacted text block]

[Redacted text block]

[Redacted text block]

[Redacted text block]

[Redacted text block]

4.3.3.6 % of Subjects Responding by Category to QUID Questionnaire Items (3 and 6 months)

For AAS, the number and percentages of subjects in each category of responses to each question on the QUID questionnaire will be reported by treatment group at each visit this questionnaire is administered.

[Redacted]

[Redacted]

[Redacted]

[Redacted]

[Redacted]

[Redacted]

[REDACTED]

[REDACTED]

[REDACTED]

[REDACTED]

[REDACTED]

[REDACTED]

[REDACTED]

[REDACTED]

[REDACTED]

[REDACTED]

- | [REDACTED]
- | [REDACTED]
- | [REDACTED]

[REDACTED]

[REDACTED]

[REDACTED]

[REDACTED]

[REDACTED]

[figure not shown]
[REDACTED]

[figure not shown]
[REDACTED]

Table 4-1 summarizes the key effectiveness analyses.

Table 4–1 Summary of Analysis Strategy for Key Effectiveness Endpoints

Endpoint	Main vs. Sensitivity Approach ^a	Statistical Method ^b	Analysis Set	Missing Data Approach
Primary				
Percentage of subjects not bothered at all by halo (on the QUID questionnaire Q2.3) at 3 months	M	Miettinen-Nurminen method	AAS	Observed data only
[REDACTED]	[REDACTED]	[REDACTED]	[REDACTED]	[REDACTED]
Secondary				
Percentage of subjects not bothered at all by glare (on the QUID questionnaire Q3.3) at 3 months	M	Miettinen-Nurminen method	AAS	Observed data only
[REDACTED]	[REDACTED]	[REDACTED]	[REDACTED]	[REDACTED]

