4.6 Handling of Missing Data

There be no imputation for missing data. The influence of missing data is expected to be minimal.

5 Safety Analysis Strategy

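### Does the plan need a rule for scoring the 3-month QUVID answer of a subject whose study lens was explanted or exchanged before Visit 4A?

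*Protocol*

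**What the plan says.** Two adjoining protocol sections deal with follow-up after a lens is removed.

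- Protocol 10.3.2 asks that every effort be made to keep a subject who stops study treatment in the trial and to "continue with the study assessments as specified in the schedule of study procedures and assessments until the final visit". The schedule (Protocol Table 3-1) has QUVID at Visits 3A, 4A and 5A.
- Protocol 10.3.3 covers explants specifically: "Subjects who discontinue IP (ie, have study lens explanted), will continue in the study through Visit 5A and be followed for safety". It adds: "At minimum, safety examinations must include the assessments associated with appropriate medical care". The bulleted examinations are visual acuity, slit lamp and dilated fundus; QUVID is not among them.

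On the analysis side, SAP 2.1 defines the All-Implanted Analysis Set (AAS) by successful implantation of a study lens and analyses effectiveness by the lens actually implanted. Table 4-1 gives "Observed data only" for the main analysis of halos, glare and starbursts. SAP 4.6 states: "There be no imputation for missing data. The influence of missing data is expected to be minimal". SAP 5.3.2 tabulates secondary surgical interventions by arm, with a category for those caused by the optical properties of the lens, and lists each one.

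**The concern.** The trial's purpose is to "compare the visual disturbance profile of the non-diffractive VIVITY IOL to two marketed diffractive EDF IOLs". Suppose a lens is removed because of its optics before the 3-month visit. The Visit 4A window runs 70 to 100 days from second-eye surgery (Protocol 10.2.9), not from the exchange, so the answer may describe a different lens. Membership of the AAS was fixed at implantation, so a favourable answer could be credited to the lens that was taken out. If QUVID is not completed, the subject leaves both numerator and denominator for a reason tied to the outcome. On neither route does the removal itself count against the lens. Compared with scoring the subject as a failure, both routes can only raise the rate of the arm that had the explant: in VIVITY's favour if the explant is in its arm, against it if in a comparator's. A borderline primary result could depend on this.

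**Working it through.** **Plan's own figures.** Protocol 8 gives 3 × 60 = 180 completers; 180 × 1.10 = 198 randomized; 198 × 1.10 = 217.8, rounded to 218 enrolled. These reproduce. The family-wise 0.05 is split as 0.05/2 = 0.025 two-sided per comparator, or 0.0125 one-sided (SAP 4; Protocol 12.4.1.2), with critical z = 2.2414. Power cannot be reproduced because the assumed rates are redacted.

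**Reading the texts together.** Protocol 10.3.2 sets the schedule; 10.3.3 sets a floor for safety examinations. A floor does not cancel the schedule, so QUVID is most naturally still collected. For attribution, SAP 2.1 ties the AAS to study implantation. A replacement that is not one of the three study lenses has no arm to be counted in, so the lens placed at study surgery is the sensible reading, though it is not spelled out.

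**Assumptions.** The documents give no explant risk r, response rate p, or chance q of a favourable answer after exchange. All three are assumed: r = 0.2%, 0.5% or 1% per subject; q = 0.5 or 1; eight rate pairs with VIVITY at 0.60–0.80 and the comparator at 0.35–0.60; 60 per arm.

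**Shift per explanted subject, compared with scoring as failure.**

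- Dropped: p/60 on average, from 0.35/60 = 0.6 points to 0.80/60 = 1.3 points.
- Answer used: q/60, which is 0.5/60 = 0.8 points, and at most 1/60 = 1.7 points.

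**Borderline example.** For a difference of zero the Miettinen-Nurminen statistic is z = (p1 − p0) / √[p(1 − p)(1/n1 + 1/n0) · N/(N − 1)], with p the pooled rate. Take the comparator at 30/60, and VIVITY with 42 successes in 58 plus two explants.

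| Handling | VIVITY | z | Lower 97.5% limit | Win |
|---|---|---|---|---|
| Both failed | 42/60 | 0.2000/0.0898 = 2.23 | −0.001 | no |
| One favourable answer used | 43/60 | 0.2167/0.0895 = 2.42 | +0.016 | yes |
| Both dropped | 42/58 | 0.2241/0.0902 = 2.49 | +0.022 | yes |

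**Averaged over whether explants occur**, with equal risk in both arms (exact binomial enumeration; ranges are over the eight rate pairs):

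| r | At least one explant in 120, 1 − (1 − r)^120 | Conclusion differs: dropped | q = 0.5 | q = 1 |
|---|---|---|---|---|
| 0.2% | 21% | 0.5–1.3% | 0.4–0.9% | 0.8–1.8% |
| 0.5% | 45% | 1.2–2.8% | 1.0–2.1% | 1.7–3.8% |
| 1% | 70% | 2.0–4.6% | 1.8–3.8% | 2.9–6.4% |

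These changes run both ways and largely cancel. At r = 1% the net change in the chance of a win is at most 1.7 points if dropped, 0.4 points at q = 0.5 and 0.7 points at q = 1.

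**Risk in one arm only**, r = 1%, true rates 0.70 against 0.50. The chance of a win when explants are failed / answer used at q = 0.5 / dropped is:

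- VIVITY only: 46.3% / 48.8% / 49.6%.
- Comparator only: 51.9% / 49.7% / 49.7%.

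Over all eight pairs the one-arm net shift reaches 2.6 points at q = 0.5 and 5.3 points at q = 1.

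**Two explants in one arm.** The conclusion then differs in 3.8–13.1% of trials if dropped, 3.1–8.8% at q = 0.5 and 6.5–17.6% at q = 1. Exactly two in 60 has probability 1770 · r²(1 − r)^58, which is 0.6%, 3.3% and 9.9% at the three risks.

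**The case for a change.** The best case for a change is that it is cheap and best settled before unmasking. The sponsor foresaw optically driven interventions, since SAP 5.3.2 has a category for them, yet that category feeds only a descriptive safety table. The expectation in SAP 4.6 that missing data matter little does not cover answers that are present but describe another lens. And at the significance boundary one rescored VIVITY subject reverses the result: against comparators of 12, 18, 24, 30 and 36 of 60, the smallest winning VIVITY counts are 24, 31, 37, 43 and 48, and one fewer loses each time.

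Part of this stands. The readable text does not state the scoring, and it does not say outright that QUVID continues after explant. But the boundary reversal holds by construction: take one success from the smallest winning count and it no longer wins.

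The natural remedy, scoring optical-cause explants as failures, is a different estimand and not plainly a better one. It would fail halos, glare and starbursts together for any optical complaint, even if halos had never bothered the subject and only one eye was exchanged. It would also make the primary endpoint depend on a cause category that unmasked staff may assign. Reasonable statisticians differ on that choice.

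**Conclusion.** No change follows. What can be shown is an unstated policy for an event of unknown but probably low frequency, which analysts can fill sensibly: collect QUVID as scheduled, use the observed answer, and attribute it to the lens placed at study surgery.

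Nor can the absence of a rule be established. The body of Protocol 12.5 on missing data, the text after the AAS definition in SAP 2.1, SAP 4.4 and 4.5, and the rows beneath each endpoint in Table 4-1 are redacted, and redacted text is not missing from the plan.

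The size rests wholly on assumed explant risks and response rates. At equal risks up to 1%, the net change in the chance of a win stays at or below 1.7 points even if subjects are dropped, and at or below 0.7 points if their answers are used. Larger shifts need the risk confined to one arm, which no document supports, and their direction depends on which arm. Only a borderline result would be affected. In that case the by-arm table and listing of secondary surgical interventions in SAP 5.3.2 would show whether any explant occurred. Clarifying Protocol 10.3.2 against 10.3.3 would tidy the wording but alter no demonstrated result.
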